5.3 Study Population

Our target population is reproductive age women with endometriosis, who are undergoing controlled ovarian hyperstimulation. Our accessible population are those seen at the University of California San Francisco Center for Reproductive Health. Our sample population are those recruited from our clinic, who meet the study criteria, and agree to participate in the study. We will also recruit a group of age-matched controls, without a history of endometriosis.

5.3.1 Number of Participants

We will be aiming for a total of 40 participants with a prior diagnosis of endometriosis. Of those 40 participants, 20 participants will be randomized to the placebo group and 20 participants will be randomized to the letrozole group. We will also enroll 20 age-matched controls without a history of endometriosis. This will result in 60 study participants.

5.3.2 Eligibility Criteria/Vulnerable Populations

Inclusion Criteria:

- Age 18-42 years
- Planning to undergo controlled ovarian hyperstimulation
- Prior diagnosis of endometriosis by one of the following: (1) surgical diagnosis (2) endometrioma on pelvic ultrasound
- Planning to freeze all retrieved oocytes/embryos prior to transfer

Exclusion Criteria:

- Hypersensitivity to Letrozole
- Any significant concurrent disease, illness, or psychiatric disorder that would compromise patient safety or compliance, interfere with consent, study participation, follow-up, or interpretation of study results

6 - Methods

6.1.1 Identity of Investigational Product/New Drug

Letrozole 5mg encapsulated oral tablet versus placebo encapsulated oral tablet.

6.1.2 Dosage, Admin, Schedule (if applicable)

Whether placed into the intervention, placebo or control group, all participants will receive their usual gonadotropin injections and trigger shot for their controlled ovarian hyperstimulation cycle, as standardly prescribed by their primary provider at the University of California Center for Reproductive health. In addition:

- The intervention group will receive oral letrozole 5 mg per day, starting on the first day of gonadotropin injections and continued until the day of trigger shot. Oral letrozole 5mg per day will be then be restarted the night of egg retrieval and continued for 2 weeks post retrieval.
- The placebo group will receive oral placebo, starting on the first day of gonadotropin injections and continued until the day of trigger shot. Daily oral placebo will be restarted the night of egg retrieval and continued for 2 weeks post retrieval.

6.1.3 Method of Assignment/Randomization (if applicable)

Patients will be randomized into either the intervention or the control group at the onset of the study. Randomization will be completed by non-clinical personnel using a computer-generated randomizer.

Safeway Palo Alto Compounding Pharmacy will be compounding and providing the encapsulated letrozole and placebo capsules. Letrozole capsules will be placed in pre-aliquoted bottles labeled A. Placebo capsules will be in pre-aliquoted bottles labeled B. Medications will be mailed to the study coordinator in batches at the start of the study. Medications will be stored at room temperature 68-77 degrees Fahrenheit and away from heat, moisture and light. The shelf life of stored medication is 12 months.

Study participants will be blinded to the content of the medication and the placebo and letrozole tablets will both be encapsulated and identical in appearance. Due to the suppressive effect of letrozole on serum estrogen levels, both providers and participants will be blinded to estradiol levels during controlled ovarian hyperstimulation. Estradiol blood draws will be obtained with each scheduled ultrasound, as routinely done during ovarian stimulation. Study participants will be counseled about this at the time of study consent and enrollment. They will be advised that at UCSF providers routinely monitor estradiol levels to guide cycle management, however many IVF clinics rely solely on ultrasound findings and do not routinely use estradiol levels. Further, when letrozole is used, estradiol levels can no longer be used for clinical management. Given letrozole is routinely used in patients with estrogen sensitive cancers undergoing ovarian stimulation without any negative impact on their cycles outcomes, we do not anticipate any negative impact from the blinding of serum estrogen levels. The cost of estrogen blood draws will be removed from the patient's IVF costs.

6.1.4 Blinding and Procedures for Unblinding (if applicable)

Patients and providers will be randomized into either the intervention or placebo group at study onset as discussed above and instructed to take medication labeled either A or B. (A) and (B) correspond to either the active ingredient medication or placebo. At completion of the study by all participants and statistical analyses of the data (based on A vs. B medication), the study coordinator will reveal patient allocation to interventional or placebo groups.

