5.1.1 Study Date Range and Duration

We anticipate it will take 12 months to enroll and complete this study. Enrollment is scheduled to begin in April of 2019 and conclude by April 2020.

The total duration per participant will be approximately 14 weeks. Participants will be asked to take letrozole or placebo throughout their ovarian stimulation and for 2 weeks following their retrieval. Participants will also be asked to complete surveys up to 12 weeks following their retrieval. Ovarian follicular fluid will be obtained at the time of egg retrieval for hormonal evaluation.

The study will involve long-term follow-up, including periodic review of participant medical records to evaluate future treatments received to treat their endometriosis and evaluate the use and outcomes of the eggs/embryos preserved during their ovarian stimulation cycle.

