6.2.2 Safety/Pregnancy-related policy

Letrazole is contraindicated during female pregnancy because of probable adverse effects on the fetus (FDA pregnancy risk category X). Pregnancy is ruled out in all women undergoing controlled ovarian hyperstimulation prior to starting stimulation medications.

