6.2.2.1 Adverse Events Definition and Reporting

Risks and side effects related to the possible use of letrozole include those which are:

Likely

- Flushing
- Mood changes
- Hot flushes
- Bloating

Less Likely

- Headache
- Fatigue
- Insomnia

Rare but serious

- Headache with vision changes
- Blood clot

Patients undergoing controlled ovarian hyperstimulation are monitored every 1-3 days by University of California Center for Reproductive Health providers. During this monitoring patients will be assessed for any possible concerns or side effects of the study medication. All concerns will be recorded and reviewed by the Data Safety and Monitoring Board on a quarterly basis.

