6.4.3.5 Interim Analysis (if applicable)

Interim analysis will not be performed. Only upon completion of all 60 participants will results be analyzed and study personnel unblinded to use of letrozole versus placebo.

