7.12 Data Safety Monitoring Plan

There will be a Data Safety Monitoring Board (DSMB) to ensure the safety of the participants and the validity and integrity of the data. The board will meet monthly to review any safety concerns raised by the study. These will include adverse events, breaches of confidentiality, unanticipated problems involving risk to participants or others.

The Data and Safety Monitoring Board, comprised of [name] (Reproductive Endocrinologist) and [name] (Reproductive Endocrinologist), will meet monthly during the study and review any safety violations or concerns generated by patients and study personnel completing the study protocols.

An adverse event (AE) is any untoward medical occurrence in a subject during participation in the clinical study or with use of the experimental agent being studied. An adverse finding can include a sign, symptom, abnormal assessment (laboratory test value, vital signs, electrocardiogram finding, etc.), or any combination of these.

A serious adverse event (SAE) is any adverse event that results in one or more of the following outcomes:

- Death
- A life-threatening event
- Inpatient hospitalization
- A persistent or significant disability/incapacity
- A congenital anomaly or birth defect
- An important medical event based upon appropriate medical judgment

AEs will be labeled according to severity, which is based on their impact on the patient. An AE will be termed "mild" if it does not have a major impact on the patient, "moderate" if it causes the patient some minor inconvenience, and "severe" if it causes a substantial disruption to the patient's well-being

AEs will be categorized according to the likelihood that they are related to the study intervention. Specifically, they will be labeled definitely unrelated, definitely related, probably related, or possibly related to the study intervention. These will be reported to the IRB on an annual basis.

Results on the progress of the study will be reported annually to the IRB and also upon the study completion. The research team will adhere to the UCSF IRB reporting requirements. No interim analysis will be completed as it would decrease the overall power of the study.

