7.15 Study Completion

Study completion is expected to occur in 6 months upon complete accrual of 60 participants. This allows for 12 weeks of follow from the enrollment of the final participant and completion of statistical analyses.

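### No authorised, logged route is stated for unblinding one participant, and the shared A/B bottle letters mean that one disclosure could decode both arms

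*Combined protocol and SAP*

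**What the plan says.** **Unblinding.** Section 6.1.4 sets the time of disclosure: "At completion of the study by all participants and statistical analyses of the data (based on A vs. B medication), the study coordinator will reveal" who received letrozole and who received placebo. Section 6.4.3.5 adds: "Only upon completion of all 60 participants will results be analyzed and study personnel unblinded to use of letrozole versus placebo". The 60 include 20 controls who take no study capsule.

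**Situations in which an assignment might be asked for.**
- Sections 3.3.1 and 6.2.2.1 list blood clot and "Headache with vision changes" as infrequent but serious risks of letrozole.
- Section 6.2.2 calls the drug "contraindicated during female pregnancy because of probable adverse effects on the fetus".
- Section 7.12 defines serious adverse events and has every event graded as "definitely unrelated, definitely related, probably related, or possibly related to the study intervention".
- Section 6.3.7 removes a participant after an untoward event that warrants it.

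None of these sections mentions access to the assignment. Nor do sections 6.4.3.3, 7.11 or 7.14.

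**Labelling.** Section 6.1.3 states that letrozole goes into bottles marked A and placebo into bottles marked B. Sections 6.1.4 and 6.1.5 treat the meaning of the letters as concealed from participants and providers. Under section 6.1.6, bottles come back to study personnel. The trial has a single site (section 5.1.2).

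**Timeline.** Section 5.1.1: "Enrollment is scheduled to begin in April of 2019 and conclude by April 2020", but also "We anticipate it will take 12 months to enroll and complete this study". Section 7.15: "Study completion is expected to occur in 6 months upon complete accrual of 60 participants", a period that includes follow-up of the last participant and the analysis.

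**The concern.** A blinded drug trial normally lets one participant's code be broken without opening the trial. Here the section that should hold that procedure describes only a disclosure for the whole study, after the analysis.

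Two things are at stake. The first is safety: the physician treating a woman with a serious event has no sanctioned way to learn whether she took letrozole. The indirect route is closed too, because providers are blinded to estradiol (section 6.1.3) and those samples are run at the end of the study (section 6.3).

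The second is the integrity of the blind. In an emergency someone is likely to find out informally, leaving no record of who learned what. With one letter per arm, that person then knows what every other bottle contains. The primary measure is a self-reported pain score, so an undocumented loss of blinding matters for interpreting any comparison of letrozole with placebo.

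**Working it through.** **1. Is there an individual route anywhere?** I read every section where one could stand.

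| Section | Content | Individual unblinding? |
|---|---|---|
| 6.1.4 | reveal after completion and analysis | none |
| 6.4.3.5 | personnel unblinded after all 60 complete | none |
| 3.3.1, 6.2.2.1 | risks, monitoring, board review | none |
| 6.2.2, 6.4.3.3 | pregnancy excluded before stimulation | none |
| 6.3.7 | removal of subjects | none |
| 7.11, 7.12, 7.14 | event reporting, safety board, stopping | none |

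**2. How long is the wait?** Let *t* be the month of enrolment and *T* the month of the reveal. The wait from enrolment is *W* = *T* − *t*.

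Inputs: accrual from April 2019 to April 2020, 12 months (5.1.1); 6 months from complete accrual to completion including analysis (7.15); about 14 weeks per participant (5.1.1).

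*Check of the plan's 6 months.* 14 weeks × 7 / 30.44 = 3.2 months, which leaves 6 − 3.2 = 2.8 months for analysis. The figure is consistent with its stated content.

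*Section 7.15 timeline.* *T* = 12 + 6 = 18.

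| Enrolled at month | Wait *W* |
|---|---|
| 0 (first) | 18 − 0 = 18 months |
| 6 (middle) | 18 − 6 = 12 months |
| 12 (last) | 18 − 12 = 6 months |

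*Section 5.1.1 timeline.* If enrolment and completion both fit into 12 months, *T* = 12 and the first woman waits 12 months. That cannot hold together with enrolment up to April 2020: anyone enrolled after month 12 − 3.2 = 8.8 would not have finished. Even with no time for analysis, *T* = 12 + 3.2 = 15.2. I therefore use the section 7.15 timeline.

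*Against the course of drug.* Each bottle holds 26 doses (6.1.5). Two weeks after retrieval take 14 of them, leaving 26 − 14 = 12 for stimulation. That split is inferred, not stated. Taking a course of about 4 weeks (0.9 months) that starts at enrolment, the wait from the end of dosing is 18 − 0.9 = 17.1 months for the first woman and 6 − 0.9 = 5.1 months for the last.

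**3. What would one disclosure reveal under the present labels?** There are 40 randomised women, 20 per arm (5.3.1), and two letters. Telling a physician that one woman took letrozole, when her bottle carries A, decodes the 20 women with A. By elimination it decodes the 20 with B as well. Physicians at the same centre manage the participants' cycles (6.1.2, 6.3), so the recipient may well be treating others in the trial.

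**The case against.** **The text does not forbid disclosure.** Section 6.1.4 says when the coordinator will reveal allocation; it does not address an individual request. The word *only* stands in section 6.4.3.5, under interim analysis, and concerns study personnel. This is right. A reader might infer that a site must refuse a physician's request, but the documents do not say so. What remains is that one route is stated and no exception is provided.

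**The assignment can be found out.** Section 6.1.3 prints the key and each woman has her bottle, so a reader who infers that nobody can learn her treatment goes too far. But that is an accidental leak that contradicts sections 6.1.4 and 6.1.5. It carries no authority, no record and no limit on recipients.

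**An exposed pregnancy is unlikely.** Pregnancy is excluded before stimulation (6.2.2, 6.4.3.3), and a freeze-all plan is an inclusion criterion (5.3.2). This stands and makes pregnancy the weaker trigger. It is not excluded: dosing runs to two weeks after retrieval, and the study schedule shows no pregnancy check before the 12-week visit. The case for serious events does not depend on it.

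**Relatedness can be graded blind.** Section 7.12 offers four grades, including probably and possibly related. This stands. The grading does not by itself show that unblinding is needed.

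**There is oversight.** A safety board reviews concerns (monthly in 3.3.1 and 7.12, quarterly in 6.2.2.1) and may stop the study (7.14). That softens the point, but no section gives the board access to one woman's assignment.

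**The consent form may cover it.** Those pages are not in the text reviewed, so this cannot be ruled out. Sections 6.1.4 and 6.4.3.5 would still need to agree with it.

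**Conclusion.** The concern holds in this form: the only unblinding that the protocol states is study-wide and follows the analysis, and no section gives an authorised, logged route for one participant. It applies to all 40 randomised women. The wait from enrolment is about 6 months for the last woman enrolled and about 18 months for the first. The 18 months is a maximum, not typical.

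The shared letters are part of the same problem. An exception alone would let one disclosure decode both arms, and the key in section 6.1.3 must be reconciled with sections 6.1.4 and 6.1.5 in any case.

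The documents do not support the stronger readings, that individual disclosure is prohibited or that the assignment is unobtainable.

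The figures assume that accrual takes the full 12 months, that section 7.15 governs the end date, and that completion means the last survey, not the open-ended chart review. The gap does not invalidate the design. It bears on participant safety and on the documentation of the blind, is cheap to close, and should be closed.

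**What to change.** 1. **Add an exception to sections 6.1.4 and 6.4.3.5.** A named, unblinded, non-clinical holder of the allocation list may disclose one participant's assignment to her treating physician, on request, for a serious adverse event or a pregnancy overlapping study drug. Log the date, reason and recipients. The participant stays in the intention-to-treat analysis of section 6.4.1, and other staff and the analysts stay blinded. The holder must be named, because the plan has non-clinical personnel randomise (6.1.3) and the coordinator reveal (6.1.4) but does not say who keeps the list.
2. **Replace the shared letters with participant-specific bottle numbers**, with the key held by the pharmacy or the list holder. Amend section 6.1.5 accordingly and remove the key from section 6.1.3, so that 6.1.3 to 6.1.5 agree. One disclosure then reveals one assignment.
3. **Have the investigators state** what follows for study drug after a disclosure. That is a clinical matter on which this review takes no position.

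The cost is relabelling by the pharmacy, a short disclosure log and a few sentences of amendment. Sample size, visits and analysis do not change.

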6.1.5 Packaging/Labelling

The study pharmacist at Safeway Palo Alto Compounding Pharmacy will make identical appearing encapsulated letrozole versus placebo pills available in a pre-aliquoted bottles. Twenty-six doses will be in each bottle and 1 bottle will be provided to the patient at the time of randomization.

The bottles will be labeled "letrozole (A)" vs. "letrozole (B)." (A) and (B) correspond to either the active ingredient medication or placebo. The study participants and providers will be blinded to the content of the medication - whether A is active or placebo medication.

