6.1.6 Storage Conditions

Medications will be stored at room temperature 68-77 degrees Fahrenheit and away from heat, moisture and light. The shelf life of stored medication is 12 months. The pharmacist will send medications in batches such that medication will be available at the time of patients starting the study but not stored for so long that the shelf life expires.

Upon returning for routing post in vitro fertilization visit, all used and unused bottles will be returned to the study personnel to assess for patient compliance. The amount of study drug dispensed and returned by the subject will be recorded. The study monitor will verify these documents throughout the course of the study.

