6.3.1 Study Schedule

M.D. Visit	
 • M.D. to identify patient as potential study participant • M.D. discusses study with patient • M.D. to notify study team if patient interested
Meet Study Team	
 • Discuss study with patient and answer questions • Subject signs study and HIPPA consents • Randomization completed, patient provided medication
Baseline Ultrasound	
 • Completion of survey #1
Stimulation Monitoring	
 • Daily letrozole/placebo starting with first day of stimulation medications • Routine uterine and ovarian ultrasound monitoring every 1-3 days at UCSF CRH • Routine blood draws for hormonal assessment every 1-3 days at UCSF CRH (patients and providers blinded to estradiol levels)
Trigger Shot	
 • Based on routine trigger shot parameters, including mean diameter of largest follicles • Completion of survey #2 • Discontinuation of letrozole/placebo
Oocyte Retrieval	
 • Retrieve all visible follicles • Follicular fluid obtained for hormonal evaluation • Restart letrozole/placebo evening of retrieval and continue daily for 2 weeks
Embryology Lab	
 • Count total number of retrieved oocytes • Count mature oocytes and fertilization rate (if making embryos) • Assess embryo quality using UCSF CRH standard grading criteria

3 Weeks Post Retrieval	
 Completion of survey #3
6 Weeks Post Retrieval	
 Completion of survey #4
12 Weeks Post Retrieval	
 Evaluation of pregnancy status Completion of survey #5
Long-term Follow-up	
 Medical record review for pregnancy outcomes of transferred embryos and additional endometriosis treatment.

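### One 26-dose bottle leaves only 11 or 12 capsules for a stimulation phase with no stated maximum, and the planned bottle count alone cannot show when supply cut the course short

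*Combined protocol and SAP*

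**What the plan says.** Section 6.1.1 describes the product as "Letrozole 5mg encapsulated oral tablet versus placebo encapsulated oral tablet", and Section 6.1.2 sets 5 mg per day, so one capsule is one day's dose.

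Section 6.1.2 has two dosing blocks. The first runs "starting on the first day of gonadotropin injections and continued until the day of trigger shot". In the second, study drug is "restarted the night of egg retrieval and continued for 2 weeks post retrieval". The table in Section 6.3.1 words the second block as "Restart letrozole/placebo evening of retrieval and continue daily for 2 weeks", and lists stopping study drug under the trigger step.

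Section 6.1.5 fixes the supply: "Twenty-six doses will be in each bottle and 1 bottle will be provided to the patient at the time of randomization".

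The length of the first block is left open. Sections 6.3, 6.3.1 and 6.3.5 tie the trigger to follicle size, and no section gives an expected or maximum number of days. Section 6.4.3.1 lists the number of stimulation days among the cycle characteristics to be compared. Section 5.1.1 gives a rough timeline: "The total duration per participant will be approximately 14 weeks", with surveys up to 12 weeks after retrieval.

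On compliance, Section 6.1.6 says that "all used and unused bottles will be returned to the study personnel to assess for patient compliance" and that the amounts dispensed and returned are recorded. It states no denominator. The return takes place at the routine post-IVF visit, which neither Section 6.1.6 nor Section 6.3.6 dates.

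**The concern.** A fixed supply is set against a requirement that varies from woman to woman. If stimulation runs long and nothing further is dispensed, the capsules run out before the 2-week post-retrieval block ends. The missing doses are the last ones scheduled, and so the exposure closest to surveys #3 to #5.

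The shortfall would depend on stimulation length, which is only known after randomisation. The compliance record as described would not reveal it: an empty bottle looks the same whether a woman finished her course or ran out. What is at stake is how well exposure in the letrozole comparison can be described. Treatment assignment is not affected.

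**Working it through.** **Inputs.** Supply is 26 capsules (6.1.5), at one capsule per day (6.1.1, 6.1.2). Let P be the post-retrieval capsules. P is 14 if the night of retrieval is the first of 14 daily doses, and 15 if it comes in addition to 14 further days. Sections 6.1.2 and 6.3.1 do not settle which, though 14 is the plainer reading. Let S be the capsule days during stimulation, which the documents do not give.

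**The plan's own figure.** The 26 cannot be derived from stated inputs, because S is missing. Solved backwards, 26 = 12 + 14 or 26 = 11 + 15.

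**Limit.** The largest S covered is 26 − P, which is 26 − 14 = 12 or 26 − 15 = 11.

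**Effect of the trigger day.** The text does not say whether a capsule is taken on that day. If it is, the latest trigger day fully covered is stimulation day 12 (P = 14) or 11 (P = 15). If it is not, the latest is day 13 or 12. The two ambiguities together move the limit between day 11 and day 13.

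**Shortfall.** Capsules due = S + P, and shortfall = max(0, S + P − 26). The values of S below are illustrations, not figures from the plan.

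| S | Due (P = 14 / 15) | Left over | Short |
|---|---|---|---|
| 9 | 23 / 24 | 3 / 2 | 0 / 0 |
| 11 | 25 / 26 | 1 / 0 | 0 / 0 |
| 12 | 26 / 27 | 0 / 0 | 0 / 1 |
| 13 | 27 / 28 | 0 / 0 | 1 / 2 |
| 14 | 28 / 29 | 0 / 0 | 2 / 3 |
| 16 | 30 / 31 | 0 / 0 | 4 / 5 |
| 18 | 32 / 33 | 0 / 0 | 6 / 7 |

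**Timeline as an indirect guide.** 14 weeks − 12 weeks leaves about 2 weeks, or 14 days, before retrieval. The interval from last stimulation capsule to retrieval is not stated. Assuming 1, 2 or 3 days gives S of about 13, 12 or 11, and a need of 27–28, 26–27 or 25–26 capsules. This suggests that 26 was chosen to fit the planned course, with little reserve. It can show no more than that: the 14 weeks is approximate, and Section 5.1.1 does not say whether it starts at consent or at the baseline ultrasound.

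**What the bottle count shows (P = 14).** A fully adherent woman with S = 12 is due 26 capsules and returns none. A woman with S = 16 is due 30, takes all 26 she was given, and also returns none, although 26/30 = 87% of her schedule was supplied. A fully adherent woman with S = 9 is due 23 and returns 3. Dispensed and returned amounts cannot place these three correctly. With S known, capsules due can be computed for each woman, and any total above 26 exposes the shortfall.

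**The case against.** The strongest reply is that no two figures contradict each other. The sum 12 + 14 = 26 is coherent, and on the plainer readings (14 post-retrieval capsules, no capsule on the trigger day) the bottle fits the planned course. That stands: this is a thin margin, not an arithmetic error.

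Second, further supply is unmentioned rather than excluded. Section 6.1.3 has the pharmacy sending medication to the coordinator in batches, in bottles labelled only A or B, so a second bottle could be found in practice. That also stands, and it is why a reader should not infer that the regimen is undeliverable. Even so, Section 6.1.5 says one bottle, and nothing tells staff what to do when it is empty.

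Third, Section 6.1.6 does not say that compliance is judged against 26. A reader might infer a fixed denominator, but the text gives none. The gap is that no denominator is stated.

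Fourth, the consequence is limited. Stimulation days are recorded, so capsules due can be reconstructed. Serum estradiol is assayed at the end of the study, and follicular fluid hormones are measured (6.3), which gives evidence of exposure during stimulation though not after retrieval. Analysis is by intention to treat (6.4.1), and no planned estimate uses the count. All of this stands. A reader might go on to infer that a null letrozole result could not be checked against exposure. The documents do not support that, because the data for a check are largely collected. What is missing is the plan to use them.

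**Conclusion.** The point holds as a small, inexpensive improvement. Followed as written, the single bottle covers 12 stimulation capsule days, or 11 if retrieval night is additional. Each further day costs one capsule at the end of the post-retrieval course. This rests only on one capsule per day, one bottle and no resupply.

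How many of the 40 randomised women would be affected is unknown. A reader might want to put a percentage on it. Assuming a normal distribution with mean 10 to 12 capsule days and SD 2, the share running out is anywhere from 11% (mean 10, limit 12) to 60% (mean 12, limit 11). The documents give neither a mean nor an SD, so that range reflects the assumptions and is not a finding about this trial. Nor do they indicate that stimulation length, and with it the shortfall, would differ between arms.

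The count of dispensed and returned capsules cannot alone tell a completed course from a truncated one. Combined with each woman's stimulation days it can, but no section plans that step. Randomisation and the intention-to-treat set are unaffected.

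**What to change.** Reconcile Sections 6.1.2, 6.1.5, 6.1.6 and 6.3.1, and state whether the trigger day and the night of retrieval count as dosing days. Which reading is intended is for the study team to decide.

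Then, without changing dose or schedule:

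- Set the bottle fill, or add an identical reserve bottle, equally for A and B, so that supply covers the schedule as written. State what staff do if a bottle is exhausted.
- In Section 6.1.6, define compliance as capsules taken divided by capsules due, with capsules due computed from each woman's recorded first gonadotropin, trigger and retrieval dates.
- Count returned capsules only after the last scheduled one, since the post-IVF visit has no stated date and could fall earlier.

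The cost is a few more capsules per woman and a short amendment, with no added participants or visits. If the post-IVF visit falls too early, the return of the bottle would have to be arranged for later.
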